10.0 Procedures Involved

10.1 Describe and explain the study design.

Once a subject has been identified, the initial visit will be scheduled. During the experimental day, informed consent will be completed, and the subjects will complete the following tasks: (1) an investigator will conduct visual acuity assessments of both eyes (Snellen). (2) The subjects will be asked to complete a survey (on contact lens satisfaction). (3) After the survey, the subject will sit with their lenses for assessment using the Keratograph topographer. (4) After topography, slit lamp assessment of the rigid lenses, and then of the cornea and conjunctiva (after lens removal) with and without Lissamine Green staining will be done.

At visit one, the following additional task will be performed: (1) The subject will be asked to sit for a corneal or scleral lens fitting visit (based on what they wear habitually), where the investigator will fit the subject with a commercially available scleral or corneal lens. All subjects will be refit into the Advanced Vision Technologies (AVT) brand of rigid lenses, manufactured at AVT Technologies in Colorado. If they already wear the AVT brand, the lens parameters will simply be re-ordered. All lenses will undergo a diagnostic fit with an AVT lens. The parameters available at AVT are similar to those available at all other major labs in the US.

A second visit will be to evaluate the fit of the ordered study lenses (which will have been coated with the HydraPEG coating), and will be for the dispense of the lenses. In addition to evaluating the lenses, the subjects will be asked to complete a short survey on their satisfaction with their current lenses. After this visit, the subjects will then wear the lenses for 30 days, on a daily basis as they habitually would, cleaning the lenses with ClearCare hydrogen peroxide cleaning system, a commonly used commercially available soft and rigid contact lens cleaner. After 30 days of lens wear, they will report for visit 3.

At the third visit, the same testing will be performed from visits 1 and 2, the subject will also be given an additional survey regarding the satisfaction with the HydraPEG lenses, and then the Tangible Boost kit or the placebo kit (consisting of

Page 9 of 22 Revised: July 24, 2017

two vials with Unique pH) solutions will be dispensed (randomized) to store their lenses in for 30 minutes that night.

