The solution will be dispensed and the subjects trained on its use, and the subjects will be asked to store their lenses in the given solution for 30 minutes that evening, and then transfer their lenses to Unique pH multipurpose rigid lens solution for overnight storage. For the initial training with the Boost or placebo system, the users will undergo an approximately 60-minute user training in which there will be visual and audio recording and still photographs taken in order for a human factors company (Userwise) to analyze the usability of the product. The investigator at the study visit will act as the monitor for the training session. This recorded training step was specifically designed to allow for proper evaluation of the usability of the product, which they will report to the FDA to ensure usability. At the initial visit, the subject will have indicated on the informed consent form whether they agree to participate in the recorded portion of the training. If they do not participate in the recording, they can still be trained and participate in the study.

The subjects will report to the Ocular Surface Institute the next day for Visit 4, at which time the comfort and visit tests will occur again, and an additional survey to evaluate the boost treatment will be given. After visit 4, the subjects will continue to wear the study lenses daily for an additional 60 days, treating their lenses again in the Boost or placebo solution at the midpoint between visit 4 and 5 (30 days after the first treatment with Boost), otherwise cleaning nightly with ClearCare, and will then report to the clinic again 30 days after the midway treatment (approximately 90 days after the initial HydraPEG dispense). The same visit testing will be done at this final and 5th visit, and a final short survey will be done, and then the lenses will be collected from the subjects and sent back to Tangible Science, Inc. for their internal testing of the lenses (no involvement of the UH research team). At this time the study will conclude.

The following table outlines each of the study visits and tells what procedures will be done at each visit:

Procedure	Length of Time Required for	Frequency of Repetition
VISIT 1: Initial Evaluation		
Informed consent & HIPAA	35 minutes	Once
General History and medications	5 minutes	Once per visit
Visual Acuity	5 minutes	Once per visit

Page 10 of 22 Revised: July 24, 2017

Questionnaires (CLDEQ8 + VAS)	10 minutes	Once per visit

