Please rate on the scale below what the quality of your vision is on an average day with the Hydra-PEG study lenses?
Poor vision, unable to Excellent vision, no
function awareness of blue
On average, how many hours each day can you comfortably wear the Hydra-PEG study lenses?

Comments:

Patient Survey: Initial Boos	t Follow-Up Visit		
Patient ID:			
Date:			
Visit #:			
Please rate on the scale be	low how comfortabl	e the study lenses were upon in	sertion today?
extremely unco	mfortable		extremely comfortable
Please rate on the scale be	low what the quality	of your vision today with the st	udy lenses?
ı			
Poor vision, u	nable to		Excellent vision, no
functio			awareness of blue
Do you prefer the current I (circle one)?	Hydra-PEG lenses or	your habitual lenses that you wo	ore prior to this study
,			
Hydra-PEG lenses	Н	abitual lenses	No preference
Did you prefer the Hydra-P	EG lenses before or	after the Boost treatment (circle	e one)?
Hydra-PEG lenses pre-Boo	st Hydra	ı-PEG lenses post-Boost	No preference
Comments:			

Patient Survey: Final Boost	t Follow-Up Visit	
Patient ID:		
Date:		
Visit #:		
Please rate on the scale be	elow how comfortable the study lenses are upon in	sertion on an average day?
extremely unco	omfortable	extremely comfortable
Please rate on the scale be average day?	elow how comfortable the study lenses are at the e	nd of the day on an
extremely unco	omfortable	extremely comfortable
Please rate on the scale be lenses?	elow what the quality of your vision is on an averag	e day with the study
Poor vision, ι		Excellent vision, no
function	on	awareness of blue

(circle one)?		
Hydra-PEG lenses	Habitual lenses	No preference
Did you prefer the Hydra-PEG lense	es before or after the Boost treatment (circ	le one)?
Hydra-PEG lenses pre-Boost	Hydra-PEG lenses post-Boost	No preference
On average, how many hours per o	day can you comfortably wear these lenses?)
Comments:		

Do you prefer the current Hydra-PEG lenses or your habitual lenses that you wore prior to this study

THE OCULAR SURFACE INSTITUTE

Subject:	

Date:	/	/
-------	---	---

Page 1 of 7

Evaluation of Tangible Boost Replenishing System

VISIT 1

1.	Time of Day (military time) ::				
2.	Signed informed consent & HIPPA: \square_1 Yes \square_2 No				
3.	Ethnicity \square_1 Hispanic or Latino \square_2 Not Hispanic or	Latino			
4.	Race ☐ American Indian or Alaskan Native ☐ Asian ☐ Black or African American ☐ Native Hawaiian or Other Pacific Islande ☐ White ☐ Other, specify				

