Over refraction (spherical only) OD OS			
OD OS			os
OS Slit Lamp Evaluation of Study Lense	es Movemei Centratio Apical Cleara	on	os

Subject:		
ate:	/	
System		

	THE O	CULA	AR SURFACE INSTITUTE	Date://
	1	Eva	luation of Tangible Boost Replenishing	g System
			Scleral Landing Zone	
11.	Perforr	n Kera	atograph NIBUT	
		OD:	NIKf-BUT "until blink" (first break up) NIKavg-BUT "until blink" (average break up) Level:	
			NIKf-BUT "25 seconds" (first break up) NIKavg-BUT "25 seconds" (average break up) Level:	
		OS:	NIKf-BUT "until blink" (first break up) NIKavg-BUT "until blink" (average break up) Level:	
			NIKf-BUT "25 seconds" (first break up) NIKavg-BUT "25 seconds" (average break up) Level:	
12.	Are len	ises st	ill adequate to be worn? \square_1 Yes \square_2 No	
If no,	, please in	ndicat	ed parameter changes indicated below:	
13.			st Training and Video recording	
	а.	Video	o file name (camera)	
			o file name (go-pro)	
	c.	Video	is uploaded to share drive? \square_1 Yes \square_2 No	

UNIVERSITY of HOUSTON

THE OCULAR SURFACE INSTITUTE

[figure not shown]
Date:	/	/
		,

Evaluation of Tangible Boost Replenishing System

[figure not shown]
- d. Videos uploaded to Dropbox?
- \square_1 Yes □₂ No
- 14. **Tangible Boost or Placebo Kit Training**
 - a. Boost/Placebo dispensed? \square_1 Yes \square_2 No
 - b. Boost Log form filled out? \square_1 Yes \square_2 No
 - c. Boost Lot #:
- **15.** Removal of lenses and Slit lamp exam (after lens removal)

Corneal Fluorescein Staining (0-4 grading) 16.

TOTAL Score: OD _____ OS ____

- Dispensed Unique pH? \square_1 Yes \square_2 No **17.**
- 18. Dispensed DMV? \square_1 Yes \square_2 No
- **Dispensed PuriLens?** \square_1 Yes \square_2 No 19.

Sub	ject:		
Date: _	/	/	

20.	Gift card given?	□₁ Ye	S	□ ₂ No	1
21.	Follow up appt in 1 day	/?	□ ₁ Ye	!S	\square_2 No
22.	Follow up appt date:				

THE	OCIII	ΔR	SLIRFA	CF	INSTITU	ITE

Subject:		
Date:	_/_	/

VISIT 4

1.	Time of Day (military time) ::					
2.	Hours of lens wear today:					
3.	Current Cleaning solution:					
4.	Currently wearing study lenses? \Box_1 Yes	\square_2 No	0			
5.	CLDEQ-8a. CLDEQ-8 completed and verified:	□₁ Yes	□ ₂ No	CLDEQ-8 score:		
6.	VAS scale a. VAS scale completed and verified:	□ ₁ Yes	□ ₂ No	VAS score:		
	b. Extended VAS scale completed:	\square_1 Yes \square_1 Yes	\square_2 No \square_2 No \square_2 No \square_2 No \square_2 No	removal:vision:		
7.	Medications a. Any changes in medications? b. If yes, please specify:		es \square_2 No			

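### The Visit 3 worksheet places kit training before the staining grade, against section 10.1, and the Visit 4 and 5 surveys call the treatment Boost in both arms

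*Combined protocol and SAP*

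**What the plan says.** **Order at Visit 3, protocol.** Section 10.1 states: "At the third visit, the same testing will be performed from visits 1 and 2". The same sentence then has the Boost or placebo kit handed out, by randomization. The visit table in section 10.1 agrees: the slit-lamp row stands above the row for kit dispensing and training.

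**Order at Visit 3, worksheet.** Item 13 is the Boost "Training and Video recording". Item 14 is headed "Tangible Boost or Placebo Kit Training" and holds "Boost/Placebo dispensed" (14a), a tick box for a Boost log form (14b) and a Boost lot field (14c). Item 15 is "Removal of lenses and Slit lamp exam (after lens removal". Item 16 is "Corneal Fluorescein Staining (0-4 grading". (The dye named in item 16 conflicts with section 10.2, which says sodium fluorescein will not be used. That is a separate matter to reconcile.)

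**Who attends the training.** Section 10.1 says of the roughly 60-minute session: "The investigator at the study visit will act as the monitor for the training session".

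**Surveys.** The initial and final follow-up surveys, used at Visits 4 and 5, carry Boost in their titles. Both ask which state of the lenses the subject preferred, "before or after the Boost treatment", with answers for pre-Boost, post-Boost or no preference. No placebo or neutral version is shown.

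**Endpoint and analysis.** Section 9.1 lists ocular surface staining among four primary endpoints. The statistical paragraph at the end of section 10.2 has each subject serve as their own control, with paired non-parametric statistics. Section 25.1 compares baseline with test data. Neither names a between-arm test or says which visit is baseline.

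**The concern.** Staining is an examiner's grade, so what the examiner knows when grading matters. The Visit 3 grade is the last one before the first soak, which takes place that evening. It is the natural reference for any change after treatment. If the worksheet is followed as numbered, that grade comes after the kit session and is written on the page that holds the lot number. The placebo is Unique pH, which the site also dispenses as the ordinary care solution. The documents do not say that the two kits look alike, that kits are coded, or that trainer and grader are different people.

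The survey wording raises a different issue. It tells a placebo subject, by implication, that the lenses were treated with the active product. Comfort ratings respond to expectation, and a pre/post comparison has no means of removing an expectation effect.

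**Working it through.** No figure in the plan is at issue, so the check is a comparison of texts followed by a short argument about where each effect would go.

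**1. Order of events**

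| Source | Lens removal, slit lamp, staining | Kit training and dispensing |
|---|---|---|
| Section 10.1, text | First | Afterwards |
| Section 10.1, visit table | Slit-lamp row above | Row below |
| Visit 3 worksheet | Items 15 and 16 | Items 13 and 14 |

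The text and the table agree with each other; the worksheet contradicts both.

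**2. Which endpoints the order touches.** On the Visit 3 worksheet the CLDEQ-8, the VAS, acuity and the Keratograph measurement all come before item 13. Only staining comes after. The order point therefore concerns one of the four primary endpoints, at one visit.

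**3. Is the Visit 3 grade still pre-treatment?** Yes. Section 10.1 has the lenses soaked that evening, and section 10.2 has training done on dummy lenses. The subject's own lenses are untreated in either order. Only the grader's knowledge could alter the score.

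**4. What that knowledge would do.** Let the Visit 3 grade be shifted by d_B in the Boost arm and d_P in the placebo arm. Change is post minus pre.

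- Between-arm difference in change: shifted by −(d_B − d_P). This is zero unless the grader knows or guesses the arm.
- Within-arm change: shifted by −d_B or −d_P, whether or not the two are equal.

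A between-arm bias thus requires arm knowledge, which the documents neither establish nor guard against.

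**5. What the survey wording would do.** Let shared expectation add e to the post-treatment rating in both arms.

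- Between-arm difference: e − e = 0.
- Within-subject change: shifted by e.

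The named analysis in section 10.2 is the second kind.

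**6. Which ratings come after the wording.** The CLDEQ-8 and the VAS on comfort at this moment do not name Boost. Within each follow-up survey the preference item comes after the comfort and vision scales. However, the survey titles stand above those scales, and the Visit 4 preference item precedes every Visit 5 rating.

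**7. Reach.** The Visit 4 and 5 wording goes to all subjects at two of five visits. Section 5.2 analyses 30 completers. The allocation ratio is not given; if it is equal (an assumption), 30 / 2 = 15 placebo subjects answer, twice each, a question whose premise is false for them.

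**The case against.** The strongest reply is that nothing here demonstrates unmasking, and most of that reply stands.

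- **The lot field.** It sits under a heading that covers both kits. Nothing says lots differ by arm or that an examiner could decode them. A reader might infer that the sheet reveals allocation; the documents do not support that.
- **The training.** Section 1.1 describes unit-dose vials, so the vials used on dummy lenses cannot be those soaked in that night, and a separate training unit is implied. Section 10.1 says the training is with the Boost or placebo system, while section 10.2 speaks only of the Boost product. A reader might infer that the investigator watches the assigned kit being opened and learns its content. That is possible but not shown.
- **The order.** Worksheet numbering is not stated to be a required sequence. The order is thus a conflict between form and protocol, not an established procedure. The form is, however, what an examiner has in hand.
- **The surveys.** Identical wording in both arms reveals nothing about allocation. Consent pages are not available for review, and section 10.2 refers to instructions on the Boost kit or placebo, so what subjects were told overall cannot be judged from a survey item. The item remains inaccurate for placebo subjects.
- **Error rates.** It is tempting to assume a rating shift and convert it into a false-positive rate. Any such shift would be invented: nothing in these forms supplies one. A pre/post test is also exposed to placebo response whatever the treatment is called, because no between-arm contrast is named. Such rates would not measure this defect.

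**Conclusion.** Two limited points hold.

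First, the Visit 3 worksheet contradicts section 10.1 on whether staining is graded before or after the kit session. If the form governs, the last pre-treatment value of one primary endpoint is graded after a session of about 60 minutes that the same investigator may have monitored, on a sheet that also carries the lot number. Loss of masking is not shown. The finding is that the documents describe no protection against it: they do not say who is masked, how kits are coded, or whether trainer and grader differ. The Boost log form is not in the text reviewed, so any coding recorded there cannot be assessed.

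Second, the Visit 4 and 5 surveys describe the treatment wrongly for placebo subjects and can raise expectation in both arms. This leaves a between-arm contrast unbiased, provided the expectation effect is equal and additive in the two arms, but it enters the within-subject comparison that the plan names.

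Neither effect can be given a numerical size from the documents. The case for acting is that the contradiction is plain and the corrections cost almost nothing.

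**What to change.** 1. On the Visit 3 worksheet, move items 15 and 16 ahead of items 13 and 14, so that the form matches the text and table of section 10.1.
2. Remove the lot field (14c) from the grading worksheet. Record the lot or kit code only on the Boost log form that item 14b already mentions, so no new log is needed.
3. In the survey titles and items, replace Boost, Boost treatment, pre-Boost and post-Boost with neutral wording such as *study solution*, *before the study solution* and *after the study solution*. The title of the Visit 3 survey also names Boost and should change with the others.

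The cost is minor form edits, with no added visits or staff. One practical consequence is that training would follow lens removal, so subjects would do it in spectacles or after reinserting their lenses. Section 10.1 already implies this order, and section 3.1 excludes anyone without usable spectacles.

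The reordering protects the Visit 3 grade only. The Visit 4 and 5 grades still depend on whether the examiner knows the kit's content, so section 10.1 should also state who is masked.

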Keratograph Surface Evaluation	5 minutes	Once per visit
Slit-lamp Examination (with lenses	10 minutes	Once per visit
on and after lens removal)		
Scleral lens / corneal lens fitting	30 minutes	Once
	100	
TOTAL TIME	100 minutes	
VISIT 2: HydraPEG dispense		
Visual Acuity	5 minutes	Once per visit
Questionnaires (CLDEQ8 + VAS	10 minutes	Once per visit
+ Secondary VAS for V2)		Shee per visit
, , , , , , , , , , , , , , , , , , ,		
Keratograph Surface Evaluation	5 minutes	Once per visit
Slit-lamp Examination	5 minutes	Once per visit
Scleral/corneal lens evaluation &	20 minutes	Once
dispense. (handling & care		
paperwork will be dispensed at this		
visit)		
TOTAL TIME		
*additional visits may be required to		
not acceptable. It is anticipated that		
Visit 1 and 2). The only tasks done		
of the lens and make any necessary of		
minutes – for a slit lamp evaluation		
determined. Since these are establish	ned wearers, we do not antici	pate a long fitting process.
VISIT 3: Tangible Boost Dispense		T
Visual Acuity	5 minutes	Once per visit
Questionnaires (CLDEQ8 + VAS	10 minutes	Once per visit
+ Secondary VAS for V3)		
Keratograph Surface Evaluation	5 minutes	Once per visit
Slit-lamp Examination	5 minutes	Once per visit
Tangible Boost kit dispense &	60 minutes	Once
training		
TOTAL TIME	85 minutes	
VISIT 4: Tangible Boost Follow-U	p #1	
Visual Acuity	5 minutes	Once per visit
Questionnaires (CLDEQ8 + VAS	10 minutes	Once per visit
+ Secondary VAS for V4)		
Keratograph Surface Evaluation	5 minutes	Once per visit
Keratograph Surface Evaluation Slit-lamp Examination	5 minutes 5 minutes	Once per visit Once per visit

Page 11 of 22 Revised: July 24, 2017

FULL PROTOCOL TITLE: An Evaluation of Tangible Boost Replenishing System on the Continued Efficacy of Tangible HydraPEG Rigid Gas Permeable Contact Lens Coating.

TOTAL TIME	25 minutes	
VISIT 5		
Visual Acuity	5 minutes	Once per visit
Questionnaires (CLDEQ8 + VAS + Secondary VAS for V5)	10 minutes	Once per visit
Keratograph Surface Evaluation	5 minutes	Once per visit
Slit-lamp Examination	5 minutes	Once per visit
TOTAL TIME	25 minutes	

10.2 Provide a description of all research procedures being performed and when they are performed.

The testing descriptions are summarized in the table below:

Test	Description	Video/Audio recording
General History and Medications	Participants will be asked questions about their general, ocular and medication use histories along with contact lens use history if applicable.	No

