Evaluation of Tangible Boost Replenishing System

	OD		OS
		_	e
		_ Comments	
erform Ker	atograph NIBUT		
OD:	NIKf-BUT "until k	olink" (first break up)	
	NIKavg-BUT "unt	til blink" (average break up)	
	Level:		
	NIKf-BUT "25 sec	conds" (first break up)	
	NIKavg-BUT "25	seconds" (average break up)	
	Level:		
OS:	NIKf-BUT "until k	olink" (first break up)	
	NIKavg-BUT "unt	til blink" (average break up)	
	Level:		
	NIKF-BLIT "25 see	conds" (first break up)	
	Level:		
			
ilit lamn eva	am (after lens remo	oval)	
iit iaiiip exe	OD	ovaij	OS
		Lids and lashes	
		Conjunctiva	
		Sclera	
		Cornea	
		Cornea 	
			

2

[figure not shown]

Subject: _____

[figure not shown]
Date: _____/_____

Evaluation of Tangible Boost Replenishing System

13. Corneal Fluorescein Staining (0-4 grading)

TOTAL Score: OD _____ OS ____

14. Gift card given? \square_1 Yes \square_2 No

Subject	•				
Dato:	1	1			

OPTIONAL VISIT FOR LENS RE-FITTING (TO BE USED IF THERE ARE FOLLOW-UP VISITS NEEDED FOR PROPER LENS FIT)

L .	Time of Day (military time) ::		
2.	Hours of Rigid lens wear today:		
3.	Current Cleaning solution:		
.	Currently wearing study lenses? \Box_1 Yes (if yes, evaluate lenses and \Box_2 No (if no, apply study lenses)	then remove and apply new ler	nses)
5.	Slit Lamp Evaluation of Study Lens test lenses if dispenses test lenses applied the habitual lenses	sed at last visit	ng evaluated)
	OD	Movement Centration Apical Clearance Limbal Clearance Scleral Landing Zone Comments	OS
.		of Study Lenses (only to be used test lenses applied today	d if test lenses for dispense were not
	OD	Movement Centration Apical Clearance Limbal Clearance Scleral Landing Zone Comments	OS
			Examiner Initials:

Page 1 of 6

Subject: _		
Date:	_/	/

DD:	OS:
Perform Ker	atograph NIBUT (to be performed only if lenses will be dispensed today)
OD:	NIKf-BUT "until blink" (first break up)
	NIKavg-BUT "until blink" (average break up) Level:
	NIKf-BUT "25 seconds" (first break up)
	NIKavg-BUT "25 seconds" (average break up) Level:
OS:	NIKf-BUT "until blink" (first break up) NIKavg-BUT "until blink" (average break up) Level:
	NIKf-BUT "25 seconds" (first break up) NIKavg-BUT "25 seconds" (average break up) Level:
Indicate CL (lesign parameter changes needed

CONTACT LENS QUESTIONNAIRE-8 (CLDEQ-8)

1. Questions about **EYE DISCOMFORT**:

- a. During a typical day in the past week, **how often** did your eyes feel discomfort while wearing your contact lenses?
 - 0 Never
 - 1 Rarely
 - 2 Sometimes

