 - **3** Frequently
 - 4 Constantly

When your eyes felt discomfort with your contact lenses, how intense was this feeling of discomfort...

b. At the end of your wearing time?

Never	Not at All				Very
have it	Intense				Intense
0	1	2	3	4	5

2. Questions about **EYE DRYNESS**:

- a. During a typical day in the past week while wearing your contact lenses, **how often** did your eyes feel dry?
 - 0 Never
 - 1 Rarely
 - 2 Sometimes
 - 3 Frequently
 - 4 Constantly

When your eyes felt dry, how intense was this feeling of dryness...

b. At the end of your wearing time?

Never	Not at All Intense				Very
have it					Intense
0	1	2	3	4	5

Patient	t/Sul	bject	#:	
Date:_	_/_	_/_	Time:	

3. Questions about CHANGEABLE, BLURRY VISION:

- a. During a typical day in the past week, **how often** did your vision change between clear and blurry or foggy while wearing your contact lenses?
 - 0 Never
 - 1 Rarely
 - 2 Sometimes
 - 3 Frequently
 - 4 Constantly

When your vision was blurry, how noticeable was the changeable, blurry, or foggy vision ...

b. At the end of your wearing time?

Never	ever Not at All ve it Intense				Very
have it					Intense
0	1	2	3	4	5

4. Question about CLOSING YOUR EYES:

During a typical day in the past week, how often did your eyes bother you so much that you wanted to close them?

- 0 Never
- 1 Rarely
- 2 Sometimes
- **3** Frequently
- 4 Constantly

5. Question about **REMOVING YOUR LENSES**:

How often during the past week, did your eyes bother you so much that you felt as if you needed to stop whatever you were doing and take out your contact lenses?

- 1 Never (please skip to question 14)
- 2 Less than once a week
- 3 Weekly
- 4 Several times a week
- 5 Daily
- 6 Several times a day

Date:
Study:
Subject #:
Visit #:
Eye: OD OS
Other Specifications:
Please rate on the scale below how comfortable your contact lenses feel at this moment.

extremely uncomfortable

extremely comfortable

Subject #:

Date:

Visit #:

Eye (circle): OD OS

4M	4M		4M		M/HC	
131	1.0	D	S	R	K	N
104	0.9	С	K	Z	0	Н
83	0.8	0	N	R	K	D
66	0.7	K	Z	V	D	С
52	0.6	V	S	Н	Z	0
42	0.5	Н	D	K	С	R
33	0.4	С	S	R	Н	N
26	0.3	S	V	Z	D	K
21	0.2	N	С	V	0	Z
16.5	0.1	R	Н	S	D	V
13	0.0	S	N	R	0	Н
10.5	-0.1	0	D	Н	K	R
8	-0.2	Z	K	С	S	N
6.5	-0.3	С	R	Н	D	V

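### CLDEQ-8 at Visit 4 mostly recalls untreated wear, and the secondary VAS changes its reference period between Visits 3 and 4, so neither measures the first soak cleanly

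*Combined protocol and SAP*

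**What the plan says.** **Timing.** Section 10.1 places the first soak at home after Visit 3: "the subjects will be asked to store their lenses in the given solution for 30 minutes that evening". Subjects then "transfer their lenses to Unique pH multipurpose rigid lens solution for overnight storage". It continues: "The subjects will report to the Ocular Surface Institute the next day for Visit 4". The Visit 3 form agrees ("Follow up appt in 1 day").

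**What is given at Visit 4.** The visit table in section 10.1 lists CLDEQ-8, the VAS and "Secondary VAS for V4". The Visit 4 form has a line "CLDEQ-8 completed and verified" with a score field.

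**CLDEQ-8 wording (appendix).** Items 1a, 2a, 3a and 4 open with "During a typical day in the past week", and item 5 also refers to the past week. Items 1b, 2b and 3b ask about intensity "At the end of your wearing time". No shorter recall period is given for Visit 4.

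**Secondary VAS (appendix surveys).** At Visit 3, insertion comfort, end-of-day comfort and vision are rated for an average day, and comfortable hours are asked. At Visit 4, insertion comfort and vision are rated for that day only, and the end-of-day and hours items are absent. Visit 5 returns to the average-day wording. Section 10.2 says these scales are unique to each visit.

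**Use.** Section 9.1 lists the comfort questionnaire as a primary endpoint without naming an instrument or visit. Section 10.2 says the questionnaires assess the coated lenses before and after Boost. Its Statistical Analysis paragraph plans paired non-parametric pre/post comparisons, with descriptive statistics with and without Boost. Section 25.1 adds a general list of methods. No pair of visits and no between-arm test is named.

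**The concern.** Visits 3 and 4 bracket the first soak, so they look like the natural before-and-after pair. CLDEQ-8 cannot serve that comparison well: by the time it is completed, almost all of its recall window is the same untreated wear that was recalled a day earlier. A flat CLDEQ-8 result at Visit 4 could then be read as no early benefit when the instrument had little chance to show one. A change in the secondary VAS between these visits would mix a change of question with any treatment effect. Section 5.3 says the data will feed power calculations for later studies, so a diluted effect estimate could be carried forward.

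**Working it through.** **1. Recall window.** Treated wear at Visit 4 is at most 1 day out of 7, so 1/7 = 14%; if half a day has been worn by the visit, 0.5/7 = 7%. At least 6/7 = 86% of the window is untreated wear.

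**2. End-of-wear items.** Section 10.1 puts the survey before the lenses are removed, and on the Visit 4 form CLDEQ-8 (item 5) precedes the slit-lamp examination after removal. Normally, then, no treated day has reached its end. As printed, items 1a, 2a, 3a and 4 run 0–4 (16 points), items 1b, 2b and 3b run 0–5 (15 points), and item 5 runs 1–6 (5 points). The span is 16 + 15 + 5 = 36, and the end-of-wear items are 15/36 = 42% of it.

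**3. Secondary VAS.** Of the four Visit 3 items, two reappear at Visit 4 with a different reference period and two are dropped. No item is identical at both visits.

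**4. Size of the dilution (illustration).** The documents give no effect size, SD, alpha or allocation ratio, so there is no plan figure to reproduce. Assume 15 per arm (30 completers, section 5.2, split equally), two-sided 5% alpha, a two-sample t-test at Visit 4, unchanged SD, and a true effect of 1.06 SD, chosen because it gives 80% power undiluted. If the treated day carries weight w, the visible effect is 1.06 × w:

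| w | Visible effect (SD) | Power |
|---|---|---|
| 1 | 1.06 | 80% |
| 1/2 | 0.53 | 29% |
| 1/3 | 0.35 | 15% |
| 1/4 | 0.26 | 11% |
| 1/7 | 0.15 | 7% |

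**5. Change score from Visit 3 to Visit 4.** This loses less, because the six shared days cancel. Take the score as a mean of seven independent daily values (SD s) plus reporting error (SD e). The change has mean effect/7 and variance 2s²/49 + 2e². Two separate weeks, the second fully treated, would give the full effect with variance 2s²/7 + 2e². The ratio of standardised effects is (1/7) × √(2/7 + 2(e/s)²) / √(2/49 + 2(e/s)²). Starting again from 80% power:

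| e/s | Ratio | Power |
|---|---|---|
| 0 | 0.378 | 19% |
| 0.2 | 0.249 | 11% |
| 0.378 (SD of a seven-day mean) | 0.189 | 8% |
| 1.0 | 0.151 | 7% |

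Paired analyses of 15 or 30 subjects, and 15 per arm, give the same power to within rounding.

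**6. What Visit 5 can show.** Soaks fall at about days 30 and 60 after dispensing, and Visit 5 at about day 90. Assume benefit proportional to remaining coating, exponential wear with half-life h, full restoration by Boost and none by placebo. Let x = 2^(−30/h). At Visit 3 both arms stand at x; at Visit 5 Boost stands at x and placebo at x³. The within-arm change under Boost is 0, even with a fully effective product. The between-arm difference is x − x³:

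- h = 15 days: 0.250 − 0.016 = 0.23
- h = 30 days: 0.500 − 0.125 = 0.38
- h = 60 days: 0.707 − 0.354 = 0.35

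This is why the Visit 5 analysis should be between arms.

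**The case against.** The strongest reply is that the harm depends on an analysis nobody has written down. The pre/post wording in section 10.2 can equally mean habitual against study lenses, and section 25.1 speaks only of baseline and test data. That stands. A reader might infer that the plan commits to testing CLDEQ-8 from Visit 3 to Visit 4; the documents do not say so. They leave that comparison open, and section 10.2's reference to lenses before and after Boost invites it.

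A second reply is that the early effect is already covered: the momentary VAS is worded identically at every visit, and same-day wording suits a one-day follow-up. This also stands. It would be wrong to conclude that comfort data at Visit 4 are unusable, or that the different secondary VAS wording is an inconsistency. The wording is disclosed and deliberate, and it does not affect a between-arm secondary VAS comparison within Visit 4. Disclosure does not, however, make Visit 3 and Visit 4 scores pairable.

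Third, subjects may give the latest day more weight than one-seventh. They may, but at half weight the illustrative power is still only 29%. Randomisation keeps the between-arm comparison at Visit 4 fair but does not restore CLDEQ-8's sensitivity.

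Finally, this is a pilot of 30 completers and the power figures rest on assumptions. Both are true. They limit the weight of the point without removing it, since the mismatch follows from the dates and wording alone.

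**Conclusion.** The point holds as a cheap improvement. CLDEQ-8 at Visit 4 has at most about one treated day in its seven-day recall, and 42% of its printed range normally cannot yet reflect treatment. It is a weak measure of the first soak whether analysed as a change from Visit 3 or between arms. The secondary VAS cannot be paired like for like between Visits 3 and 4. These conclusions need no assumption beyond the visit timing, test order and printed questions.

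The power figures do rest on assumptions (15 per arm, 5% two-sided alpha, a chosen effect, stated weights, independent days) and show direction and rough size only. The problem is confined to Visit 4: the CLDEQ-8 recall week at Visit 5 lies wholly after treatment, so a reader should not conclude that the comfort endpoint as a whole is compromised.

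**What to change.** 1. Name the existing momentary VAS as the Visit 4 comfort outcome, compared between arms with the Visit 3 value as baseline.
2. Assess the Boost effect on CLDEQ-8 as the between-arm difference at Visit 5, adjusted for Visit 3. Report CLDEQ-8 at Visit 4 descriptively only.
3. Add the Visit 4 same-day items on insertion comfort and vision to the Visit 3 survey, or state that the Visit 3 and Visit 4 secondary VAS will not be paired.

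This takes a few sentences of analysis text and, if items are added, two survey lines. No new visit or instrument is needed.

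The costs should be stated openly. The immediate effect would rest on a single-item VAS. Visit 5 is about 30 days after the second soak, so under the wear model above the between-arm contrast keeps only about 0.23 to 0.38 of the fresh-coating benefit. With an assumed 15 per arm, 80% power is reached only for about 1.06 SD of that contrast, or 1.06 × √(1 − 0.5²) = 0.92 SD with an assumed baseline correlation of 0.5. Without adjustment, that corresponds to a fresh-coating benefit of roughly 1.06/0.375 = 2.8 to 1.06/0.234 = 4.5 SD. Visit 5 is the better-matched CLDEQ-8 comparison, but it is not a sensitive one at this sample size.
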